electronic medical records for opioid consumption in PACU and ward; pain scores before surgery, in PACU and ward; requirement of oxygen in PACU and ward; nausea and vomiting, requirement of antiemetics, requirement of naloxone, and adverse events. Patient interaction with presented video content will be characterized using eye-tracking metrics.

Outcomes

All postoperative assessment will be made by an investigator who is strictly blinded to treatment allocation, and actual treatment (e.g., full immersion or sham distraction).

Primary Outcome

1. **Pain Scores.** We will assess pain using NRS scores (0-10, with 10 being worst) immediately before and 15 minutes after each intervention with the device, starting on postoperative day one (POD1) and until end of postoperative day two (POD2) or hospital discharge, whichever occurs first.

Secondary Outcomes

1. **Total opioid consumption.** We will measure total opioid consumption, converted to morphine milligram equivalents (MME), starting at the first pre-intervention pain score measurement, postoperative day one (POD1), and until the end of postoperative day 2 (POD2) or hospital discharge, whichever occurs first.
2. **Pain scores.** We will capture all pain score measurements done every 4 hours by standard of care starting at the first pre-intervention pain score measurement, POD1, and end of postoperative day two or hospital discharge, whichever occurs first, using NRS scores (0-10, with 10 being worst). Only the pain scores from routine nurse assessments will be used here (pain scores measured as a part of the primary outcome won't be included).
3. **Perception of video system usability.** Patient's perception of video system

Virtual Reality Distraction for Reduction in Acute Postoperative Pain

usability will be assessed using a validated questionnaire (System Usability Scale¹³) once after the last intervention with the device and before hospital discharge. The System Usability Scale is scored from 0 to 100 and higher scores are related with devices that are easier to use.

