Primary outcome. We will assess the effect of VR on NRS pain score after each study treatment over postoperative days one and two using a linear mixed effects model on the series of post-VR pain scores while adjusting for the corresponding pre-VR pain score, with time and randomized group as fixed effect categorical variables. We will adjust for within-subject correlation across the pain scores using either an autoregressive AR (1) or unstructured correlation matrix, whichever has better fit (lower AIC, BIC). We will assess the group-by-time interaction, but even if significant ($P < 0.15$) the primary result will be made collapsing over time.

Secondary Outcomes

1. **Total opioid consumption.** We will assess the effect of VR on log-transformed total opioid consumption starting at the first pre-intervention pain score measurement, POD1, and until end of postoperative day 2 or hospital discharge, whichever occurs first, using a linear regression model.
2. **Pain scores.** We will assess the effect of VR on pain score over time starting at the first pre-intervention pain score measurement, POD1, and until end of postoperative day 2 or hospital discharge, whichever occurs first, using a linear mixed effects regression to account for within-subject correlation. Only the pain scores from routine nurse assessments will be used here (pain scores from Aim 1 won't be used).
3. **Perception of video system usability.** We will assess the effect of VR on perception of video system usability as measured by the System Usability Scale using a Wilcoxon rank-sum test and report the median difference (along with the 95% CI) estimated using the Hodges-Lehmann approach.
4. **Post discharge analgesia.** We will assess the effect of VR on analgesia scores one week after discharge using a Wilcoxon rank-sum test and report the median

Virtual Reality Distraction for Reduction in Acute Postoperative Pain

difference (along with the 95% CI) estimated using the Hodges-Lehmann approach.

Tertiary Outcomes

5. **Anti-emetic medications.** We will assess the effects of VR on the number of times a patient required anti-emetic medication within starting at the first pre-intervention pain score measurement, POD1, and until postoperative day 2 or hospital discharge, whichever occurs first, using a Wilcoxon rank-sum test, and report the median difference (along with the 95% CI) estimated using the Hodges-Lehmann approach.

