Strongly disagree 	Disagree 	Neutral 	Agree 	Strongly agree 
10. I need to learn a lot of things before I could get going with this product				
Strongly disagree 	Disagree 	Neutral 	Agree 	Strongly agree 

Virtual Reality Distraction for Reduction in Acute Postoperative Pain

System Usability Scale assessment scoring

	Strongly disagree	Disagree	Neutral	Agree	Strongly agree	SCORE
I think that I would like to use this product frequently	1	2	3	4	5	(score) – 1
I found the product unnecessarily complex	1	2	3	4	5	5 – (score)
I thought the product was easy to use	1	2	3	4	5	(score) – 1
I think that I would need the support of a technical person to be able to use this product	1	2	3	4	5	5 – (score)
I found that the various functions in this product were well integrated	1	2	3	4	5	(score) – 1
I thought that there was too much inconsistency in this product	1	2	3	4	5	5 – (score)
I would imagine that most people would learn to use this product very quickly	1	2	3	4	5	(score) – 1
I found the product very awkward to use	1	2	3	4	5	5 – (score)
I felt very confident using the product	1	2	3	4	5	(score) – 1
I need to learn a lot of things before I could get going with this product	1	2	3	4	5	5 – (score)
TOTAL SCORE: 0 (worst outcome) to 100 (best outcome)	Sum of the scores for each statement and multiply by 22.5 55 raw score: P25%, 68 raw score: P50%, 75 raw score: P75%					

Virtual Reality Distraction for Reduction in Acute Postoperative Pain

G. REFERENCES

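### The usability scoring rule multiplies the item sum by 22.5, which gives a 0–900 scale; the stated 0–100 scale needs 2.5

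*Combined protocol and SAP*

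**What the plan says.** Section 3.E (Measurements), Secondary Outcomes item 3, names the instrument: "usability will be assessed using a validated questionnaire (System Usability Scale". It is given once, after the last device session and before discharge. The same item fixes the scale: "The System Usability Scale is scored from 0 to 100 and higher scores are related with devices that are easier to use".

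Section 3.F (Data Analysis), Secondary Outcomes item 3, plans to compare the arms on "usability as measured by the System Usability Scale using a Wilcoxon rank-sum test and report the median difference (along with the 95% CI", with the estimate obtained by the Hodges-Lehmann approach.

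Addendum C gives the scoring table. Responses run from 1 to 5. Five items are scored as the response minus 1, and the other five as 5 minus the response. The final row holds three statements:

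- the range: "TOTAL SCORE: 0 (worst outcome) to 100 (best outcome";
- the calculation: "Sum of the scores for each statement and multiply by 22.5";
- reference percentiles: "55 raw score: P25%, 68 raw score: P50%, 75 raw score: P75".

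No other part of the document gives a multiplier or a later rescaling step.

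**The concern.** The calculation and the range in that final row cannot both be right. Ten items worth at most 4 points each sum to 40, and 22.5 times 40 is far above 100.

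This matters because the row is the plan's only instruction for deriving the score, so it is what someone building the form or writing the scoring program would follow. The plan commits to reporting an estimated difference with a 95% confidence interval on the instrument's own scale, and that scale is what gives the estimate meaning. An estimate on a 0–900 scale presented as 0–100 would badly mislead a reader about its size. It could not be set against the percentiles printed beside the rule, or against any other result on a 0–100 scale.

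**Working it through.** **Inputs, all from the Addendum C scoring table unless noted**

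- Ten items, responses 1 to 5.
- Five items scored as response − 1; five scored as 5 − response.
- Multiplier 22.5.
- Stated total 0 to 100 (also in Section 3.E).
- Reference values 55, 68 and 75.

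**Step 1. Range of the item sum**

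- Response − 1: from 1 − 1 = 0 to 5 − 1 = 4.
- 5 − response: from 5 − 5 = 0 to 5 − 1 = 4.
- Sum: minimum 5 × 0 + 5 × 0 = 0; maximum 5 × 4 + 5 × 4 = 40.

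**Step 2. Try to reproduce the stated 0–100**

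| Rule | Minimum | Maximum |
|---|---|---|
| Recoded sum × 22.5 (as printed) | 0 | 40 × 22.5 = 900 |
| Unrecoded responses summed (10–50) × 22.5 | 225 | 1125 |
| Mean recoded item (0–4) × 22.5 | 0 | 90 |
| Recoded sum × 2.5 | 0 | 40 × 2.5 = 100 |

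The stated range is not reproduced by 22.5 under any of these readings. The implied multiplier is 100 / 40 = 2.5, and it reproduces the range exactly. The ratio of the two multipliers is 22.5 / 2.5 = 9.

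**Step 3. Check against the printed percentiles**

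| Printed value | Item sum implied at × 2.5 | Item sum implied at × 22.5 |
|---|---|---|
| 55 | 22.0 | 2.4 |
| 68 | 27.2 | 3.0 |
| 75 | 30.0 | 3.3 |

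At 2.5 the three values fall at 22 to 30 out of 40. At 22.5 they would all lie between 2 and 4 out of 40, which is implausible for the lower quartile, median and upper quartile of a usability score. The percentiles therefore also point to 2.5. They are labelled as raw scores, which cannot be right either, because the recoded sum stops at 40 and the unrecoded sum at 50.

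**Step 4. What literal use would do**

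- A patient answering neutral throughout has a sum of 10 × 2 = 20. The score would be 20 × 22.5 = 450 instead of 20 × 2.5 = 50.
- A sum of 4 gives 90, already above the printed 75th percentile. A sum of 5 gives 112.5, above the stated maximum. Only sums of 0 to 4 stay within 0–100.
- A difference of 5 points becomes 5 × 9 = 45. The printed median of 68 would scale to 68 × 9 = 612. Scores move in steps of 2.5, so 68 itself cannot be attained; the nearest attainable score, 67.5, becomes 607.5.

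**Step 5. Effect on the planned analysis**

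Multiplying every score in both arms by the same positive constant leaves the ranks unchanged, so the Wilcoxon P value does not move. The Hodges-Lehmann estimate is the median of all between-arm pairwise differences, so it and its confidence limits scale by that constant. An illustrative simulated data set with 56 patients per arm showed this: P = 0.2745 under both multipliers, and an estimated difference of 2.5 under one and 22.5 under the other.

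**The case against.** The best case against giving this weight is that the slip exposes itself. The correct range stands in the same row and again in Section 3.E, and the percentiles follow directly after the multiplier. Under the printed rule any item sum of 5 or more exceeds the stated maximum, so nearly every score would look impossible. The error is common to both arms: the P value, the direction of effect and whether the interval excludes zero are all unchanged, and dividing by 9 restores the right figures with no loss of data. No planned analysis classifies patients by 55, 68 or 75. Usability is listed among the secondary outcomes but is not one of the two secondary hypotheses in Section 2. Finally, a stray digit could have entered when the text of a crowded table cell was copied, so the source page should be consulted.

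Most of this stands as a limit on the consequences. None of it removes the contradiction. Nothing positive suggests a copying fault: the neighbouring numbers are intact. The document describes no range check, so detection would depend on someone noticing. Being easy to notice is also a reason to correct the rule now, not to leave it for the analyst to resolve.

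**Conclusion.** The concern holds. On the text as it reads, the only scoring rule for this secondary outcome yields 0–900, against a stated 0–100. Only a multiplier of 2.5 reconciles the item coding with that range.

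The size of the error is exactly a factor of 9 on scores, medians, the estimated difference and its confidence limits, and it arises only if the rule is applied literally. Tests, the primary outcome, the sample size and the interim boundaries are unaffected. This is most likely a typing error. It should be corrected because it sits in the operative definition of a reported estimate.

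The conclusion rests on two things: that the item recoding and the 0–100 range, which agree with each other and with the percentiles, are what was intended; and that the source page does read 22.5. The document does not show whether the case report form or scoring program carries the error.

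**What to change.** 1. Check the source page, then change the multiplier in the last row of the Addendum C scoring table from 22.5 to 2.5.
2. Confirm that the case report form and any scoring program use 2.5. If scores have already been derived, confirm that they lie within 0–100; any derived with 22.5 can be divided by 9.
3. In the same edit, drop the raw-score label from 55, 68 and 75 and describe them as values on the 0–100 scale.

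The cost is a one-number correction, a relabelling and a short confirmation. No change to design, data collection or analysis method is needed.
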